## 12.6 Clinical Laboratory Tests (Chemistry, Hematology, and Urinalysis)

Clinical Laboratory Panels	Time Point		
	Period	CRF/Listing Day and Hour	Table
Chemistry, Haematology,	Screening		NA
Urinalysis	Check-in	Day -1 Hour -22.50	Baseline
	5	Day 1 Hour 8.67	End of Study

Clinical laboratory tests will be measured at the following time points:

Time points in the CRF/Listing column are approximated/based on the blank CRF and it should be noted that the data listings will reflect the data found in the final subject CRFs.

If applicable, an early termination assessment will be performed.

NA = Not applicable (individual result(s) may be required for baseline)

Clinical laboratory results will be presented in standard international (SI) units. Out-ofreference range flags will be recorded as follows: high (H) and low (L) for numerical results and did-not-match (\*) for categorical results.

Out-of-reference range values and corresponding recheck results will be listed.

For all numeric laboratory values, descriptive statistics will be presented for each laboratory test by assessment time point. Change from baseline will be summarised in a similar manner. For all numeric laboratory tests, the mean value calculated for each assessment time point will be compared to the reference range and flagged if outside of the reference range (\* if

above the reference range and ^ if below the reference range). In the event there is more than one reference range for a laboratory test, the comparison will be made against the lowest of the lower ranges and the highest of the higher ranges.

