6.4.4.5 Clinical Laboratory

All clinical laboratory tests will be conducted by an accredited laboratory. Values for the clinical laboratory parameters are to be within the laboratory normal ranges or deemed not clinically significant in the opinion of the Investigator. All tests listed below will be performed as delineated in the Study Events Flow Chart (Table 1). Up to approximately 38 mL of blood will be drawn from each subject during the entire study for clinical laboratory tests.

Serum Chemistry¹

- Albumin
- Alkaline phosphatase
- Alanine aminotransferase
- Aspartate aminotransferase
- Bicarbonate
- Blood urea nitrogen
- Creatinine
- Glucose
- Potassium
- Sodium
- Total protein
- Uric acid

Urinalysis²

- Bilirubin
- Blood
- Glucose
- Ketones
- Leukocyte esterase
- Nitrite
- pH
- Protein
- Specific gravity
- Urobilinogen

Additional Tests

- Serology
 - HIV
 - HBsAg
 - HCV
- Serum pregnancy test³
- Serum FSH⁴
- Urine cotinine
- Urine drug screen
 - Amphetamines
 - Cannabinoids
 - Cocaine
 - Opiates
- Urine/breath alcohol

Hematology

- Hematocrit
- Hemoglobin
- Platelet count
- Red blood cell count
- White blood cell count with differential

¹ Serum chemistry tests will be performed after at least an 8-hour fast; however, in case of dropouts or rechecks, subjects may not have fasted for 8 hours prior to the serum chemistry sample being taken. For the samples collected at EOS, an 8-hour fast is not required.

² A microscopic examination for red blood cells, white blood cells, bacteria, and casts will be performed if an abnormality is noted in leukocyte esterase, protein, blood, or nitrite.

³ Human chorionic gonadotropin (females only).

⁴ For postmenopausal females only.

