## **12. SAFETY**

All relevant case report form (CRF) and clinical laboratory data will be listed by subject and chronologically by assessment time point. This will include rechecks, unscheduled, and early termination assessments.

Applicable continuous variables will be summarised using n, mean, SD, minimum, median, and maximum.

The level of precision will be presented as follows: minimum/maximum in the same precision as in the database, mean/median in one more precision level than minimum/maximum, SD in one more precision level than mean/median, and n will be presented as an integer. Percentages will be presented as an integer.

Where individual data points are missing because of dropouts or other reasons, the data will be summarised based on reduced denominators.

Baseline will be the result closest and prior to the first product use on Day 1 unless otherwise stated. Summaries for post-baseline time points will not include rechecks, unscheduled, or early termination measurements.

Tables summarising safety data by assessment time point will only include summaries for baseline and post-baseline time points.

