# = Lowest of the lower ranges and highest of the higher ranges are used. Refer to Appendix 16.1.10 for the breakdown.

\* = Above reference range; ^ = Below reference range EOS = End of study

Source: ADaM.< > Program: /CAXXXX/sas\_prg/stsas/tab/programname2022Q1.sas DDMMMYYYY HH:MM

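### The laboratory summary tables flag a pooled group mean against a range meant for individuals, and no table counts the subjects out of range or their shift from baseline

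*SAP*

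**What the plan says.** SAP section 12.6 sets the rule for numeric tests: "the mean value calculated for each assessment time point will be compared to the reference range and flagged" if it lies outside, with an asterisk for above and a caret for below. Where a test has more than one reference range, "the comparison will be made against the lowest of the lower ranges and the highest of the higher ranges". The footnote of shell CLBD, which produces Tables 14.3.5.1 to 14.3.5.3, repeats this: "Lowest of the lower ranges and highest of the higher ranges are used". The reference-range listing (Appendix 16.1.10) has columns for sex and age category.

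The same section also handles individual results. Each numeric result is marked H or L, and "Out-of-reference range values and corresponding recheck results will be listed". Tables 14.3.4.1 to 14.3.4.3 (shell CLBO) carry that listing, and the by-subject laboratory reports follow in Appendix 16.2.8. On summary statistics, SAP section 12 says "Applicable continuous variables will be summarised using n, mean, SD, minimum, median, and maximum". CLBD prints these beside the reference range and adds change from baseline. Laboratory tests have two table time points: baseline at check-in, and End of Study on the last product day.

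The protocol leaves clinical relevance to the Investigator. Its section 6.4.4.5 states: "Values for the clinical laboratory parameters are to be within the laboratory normal ranges or deemed not clinically significant". Its section 6.4.5 counts an abnormal laboratory finding as a possible adverse event.

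**The concern.** A reference range is built to hold most individual values. A mean of 25 subjects has a sampling SD of SD/√25 = SD/5, so it stays well inside that range unless the whole group moves a long way. Pooling both sexes and using the outermost limits can move the flag point further still. A sizeable minority of subjects could therefore leave their own range while the summary row stays unflagged.

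The quantity a reader of a safety summary wants is how many subjects were in range at baseline and out of range afterwards. No table gives it. Safety and tolerability is a stated secondary objective, and adverse events, by contrast, are tabulated as number and percent of subjects.

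**Working it through.** **Inputs.** n = 25 (protocol synopsis and section 3.1). The documents give no laboratory limits, means, SDs or sex mix, and no intended operating point for the flag, so there is no figure of the plan's to reproduce. Assumed: the range is the central 95% (mean ± 1.96 SD), values are normal or lognormal, the upper limits of the two sexes are 0 to 1.5 SD apart, and 50% or 100% of subjects are women.

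**Step 1: one range, normal values, shift upward.** If a share f of subjects lies above the upper limit, that limit is z(1−f) SD above the mean, and P(flag) = 1 − Φ(5 × z(1−f)).

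| Share above limit | P(mean flagged) |
|---|---|
| 20% | about 0 |
| 30% | 0.4% |
| 40% | 10% |
| 45% | 26% |
| 50% | 50% |
| 60% | 90% |

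Example: for 30%, z = 0.524, 5 × 0.524 = 2.62, and 1 − Φ(2.62) = 0.0044.

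In terms of shift:
- 1 SD puts 25 × [1 − Φ(0.96)] = 4.2 subjects above the limit, with P(flag) about 0.
- 1.5 SD puts 25 × [1 − Φ(0.46)] = 8.1 above, with P(flag) = 1 − Φ(5 × 0.46) = 1 − Φ(2.3), about 1%.
- If only 20% of subjects are affected, each must move 1.96/0.2 = 9.8 SD before the expected mean reaches the limit.

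**Step 2: several ranges, outermost limits used.** Let the women's centre and upper limit lie d SD below the men's, with a common shift s.
- Half women: the pooled mean reaches the higher limit when s − d/2 = 1.96, so the share above their own limit is Φ(d/2).
- All women: the share is Φ(d).

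| d (SD) | Half women | All women |
|---|---|---|
| 0 | 50% | 50% |
| 0.5 | 60% | 69% |
| 1.0 | 69% | 84% |
| 1.5 | 77% | 93% |

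**Step 3: skewed values.** For a lognormal test with log-scale SD σ, the share above the limit when the mean equals the limit is 1 − Φ(σ/2): 46% (σ = 0.2), 44% (0.3), 40% (0.5), 35% (0.8), 31% (1.0). Simulation with n = 25 and σ = 0.8 (100,000 runs) gives P(flag) = 26% with 30% of subjects above the limit and 70% with 40%.

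**Step 4: a few extreme values.** If k subjects are extreme and the others sit at half the upper limit, each extreme subject needs (25 − 0.5 × (25 − k))/k times the limit to bring the mean to it: 13 times for k = 1, 6.75 times for k = 2, 3 times for k = 5.

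**Step 5: wider spread in both directions.** If the SD triples with no shift, 2 × [1 − Φ(1.96/3)] = 51% of subjects are out of range, and P(flag) = 2 × [1 − Φ(5 × 1.96/3)] = 0.1%.

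The same mark can therefore stay absent with half the subjects out of range on one test and appear for one subject in 25 on another.

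**The case against.** A reader might infer that the SAP judges laboratory safety by this flag, so that an unflagged table means no signal. The documents do not support that. The flag annotates a descriptive table, and nothing in the SAP rests a conclusion on it. Every out-of-range value appears with its recheck in a Section 14 display, identified by period, day, hour and date, and with 25 subjects that display can be read subject by subject. CLBD shows the minimum, maximum and SD, where a small extreme subgroup would stand out, and a common shift of 1 or 1.5 SD would appear in its change-from-baseline column. The Investigator assesses individual values, and any abnormality reported as an adverse event is counted by subject in Table 14.3.1.1.

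Three further limits are fair. The half-of-subjects threshold depends on symmetric values moving one way. The widened range applies only to tests with more than one range, and where one range contains the others it is simply that range. Protocol section 2.2 makes laboratory summary statistics optional, so the SAP meets its commitment.

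All of this stands, and it keeps the point small. It does not rescue the rule, which still compares a mean with limits for individuals. Nor does it supply the missing count: a maximum shows that someone was high, but not how many, nor whether they were in range at baseline.

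**Conclusion.** The point holds as a minor one. The mean flag in SAP 12.6 and CLBD is on the wrong scale and has no stable meaning. For roughly symmetric tests shifting in one direction it is unlikely to appear until about half the subjects are out of range, and more where widened limits apply (60% to 69% for sex limits 0.5 to 1 SD apart and equal sexes). For skewed tests 31% to 46% can be enough, and a few extreme values can set it off. These sizes rest on an assumed central-95% range and assumed distributions, because the documents give no laboratory values.

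Individual abnormalities are not lost. What is missing is a table of the number and percent of subjects out of range, and of their shift from baseline.

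**What to change.** In SAP 12.6 and shell CLBD, replace the mean-versus-range flag, and with it the widened range, with n (%) of subjects low, normal and high at End of Study by baseline category for each numeric test. Use each subject's own sex- and age-specific range and the H and L flags already derived. Keep the descriptive statistics and the listings.

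If the mean flag is kept, add a footnote that its absence does not show that individuals were in range. Also reconcile the symbols: the CLBD programmer note uses an asterisk for both above and below, while SAP 12.6 and the CLBD footnote use an asterisk for above and a caret for below.

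The cost is SAP wording, one shell and a few more table rows, with no new data. Isolated out-of-range values in healthy subjects will become visible in the summary. The counts cannot be attributed to a single product, because the table has only a baseline and one time point after all five products, and a footnote should say so.

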## 12.7 Vital Signs

Vital signs will be measured at the following time points:

Parameter	Time Point			
	Period	CRF/Listing Day and Hour	Table	
	Screening		NA	
	Check-in	Day -1 Hour -22.00	NA	
Blood Pressure, Pulse,	1	Day 1 Hour -0.50	Baseline	
Respiration, Temperature	2	Day 1 Hour -0.50	Day 2 Preuse	
	3	Day 1 Hour -0.50	Day 3 Preuse	
	4	Day 1 Hour -0.50	Day 4 Preuse	
	5	Day 1 Hour -0.50	Day 5 Preuse	
Blood Pressure, Pulse	5	Day 1 Hour 8.50	End of Study	

Time points in the CRF/Listing column are approximated/based on the blank CRF and it should be noted that the data listing will reflect the data found in the final subject CRFs.

If applicable, an early termination assessment will be performed.

NA = Not applicable (individual result(s) may be required for baseline)

Descriptive statistics will be presented for vital signs measurements by assessment time point. Change from baseline will be summarised in a similar manner.

#### 12.8 Electrocardiogram

ECGs will be measured at the following time points:

Parameter	Time Point		
	Period	CRF/Listing Day and Hour	Table
HR, RR, PR, QRS, QT,	Screening		NA
QTcF	Check-in	Day -1 Hour -22.25	Baseline
	5	Day 1 Hour 8.33	End of Study

Time points in the CRF/Listing column are approximated/based on the blank CRF and it should be noted that the data listing will reflect the data found in the final subject CRFs.

If applicable, an early termination assessment will be performed.

NA = Not applicable (individual result(s) may be required for baseline)

Descriptive statistics will be presented for ECG measurements by assessment time point. Change from baseline will be summarised in a similar manner.

All ECG data will be listed by subject where QTc values > 450 msec and increase from baseline > 30 msec will be flagged.

#### 12.9 Prior and Concomitant Medications

Prior and concomitant medications recorded during the study will be coded with the World Health Organization (WHO) Drug Dictionary Version 01-Sep-2023\_b3 and listed.

#### 12.10 Oral and Physical Examination

Abnormal physical examination findings will be reported as medical history or AEs. All data found in the CRF will be listed.

## 12.11 Exhaled Carbon Monoxide

Exhaled Carbon Monoxide (CO) levels will be measured using a Bedfont Micro+ Smokerlyzer or similar device, at Screening and at Check-in. Exhaled CO data will be listed by subject and assessment timepoint.

## 12.12 Device Malfunction

Incidence of device malfunction(s) will be listed by subject and tabulated by product.

# 13. SUMMARY OF CHANGES FROM PROTOCOL-PLANNED ANALYSIS

The analyses described in this SAP are aligned with those analyses described in the protocol.

# 14. SUMMARY TABLES, FIGURES, AND LISTINGS

Summary tables, figures, and listings are numbered following the International Council on Harmonization (ICH) structure but may be renumbered as appropriate during the compilation of the tables and figures for the CSR. Note that summary tables, figures, and listings will be generated using SAS® Version 9.4 or higher, as appropriate.

#### 14.1 Section 14 Tables and Figures

The following is a list of table and figure titles that will be included in Section 14 of the report. Table and figure titles may be renumbered as appropriate during the compilation of the report.

Number	Title	Shell
Table 14.1.1	Disposition Summary (Safety Population)	CDS
Table 14.1.2	Subject Product Use Status and Study Disposition (Safety Population)	SDS
Table 14.1.3	Demographic Summary (Safety Population)	CDEM

#### 14.1 Demographic Data Summary Tables

Number	Title	Shell
Table 14.1.4	Smoking History and Usual Brand Attributes Summary (Safety Population)	CSHUB

# 14.2 Pharmacokinetic, Subjective Effects, Topography, and Product Use Behaviour Summary Tables and Figures

# 14.2.1 Pharmacokinetic Tables – Plasma Nicotine

Number	Title	Shell
Table 14.2.1.1	Unadjusted Plasma Nicotine Concentrations (ng/mL) Following Controlled Product Use of Stick (Outcomes Population)	CPConc1
Table 14.2.1.2	Unadjusted Plasma Nicotine Concentrations (ng/mL) Following Controlled Product Use of Stick (Outcomes Population)	CPConc1
Table 14.2.1.3	Unadjusted Plasma Nicotine Concentrations (ng/mL) Following Controlled Product Use of Stick (Outcomes Population)	CPConc1
Table 14.2.1.4	Unadjusted Plasma Nicotine Concentrations (ng/mL) Following Controlled Product Use of Stick (Outcomes Population)	CPConc1
Table 14.2.1.5	Unadjusted Plasma Nicotine Concentrations (ng/mL) Following Controlled Product Use of Subject's OBCC (Outcomes Population)	CPConc1
Table 14.2.1.6	Baseline-Adjusted Plasma Nicotine Concentrations (ng/mL) Following Controlled Product Use of Stick (Outcomes Population)	CPConc1
Table 14.2.1.7	Baseline-Adjusted Plasma Nicotine Concentrations (ng/mL) Following Controlled Product Use of Stick (Outcomes Population)	CPConc1
Table 14.2.1.8	Baseline-Adjusted Plasma Nicotine Concentrations (ng/mL) Following Controlled Product Use of Stick (Outcomes Population)	CPConc1
Table 14.2.1.9	Baseline-Adjusted Plasma Nicotine Concentrations (ng/mL) Following Controlled Product Use of Stick (Outcomes Population)	CPConc1

Table 14.2.1.10	Baseline-Adjusted Plasma Nicotine Concentrations (ng/mL) Following Controlled Product Use of Subject's OBCC (Outcomes Population)	CPConc1
Table 14.2.1.11	Baseline-Adjusted Plasma Nicotine Pharmacokinetic Parameters Following Controlled Product Use of Stick (Outcomes Population)	CPPar1
Table 14.2.1.12	Baseline-Adjusted Plasma Nicotine Pharmacokinetic Parameters Following Controlled Product Use of Stick (Outcomes Population)	CPPar1
Table 14.2.1.13	Baseline-Adjusted Plasma Nicotine Pharmacokinetic Parameters Following Controlled Product Use of Stick (Outcomes Population)	CPPar1
Table 14.2.1.14	Baseline-Adjusted Plasma Nicotine Pharmacokinetic Parameters Following Controlled Product Use of Stick (Outcomes Population)	CPPar1
Table 14.2.1.15	Baseline-Adjusted Plasma Nicotine Pharmacokinetic Parameters Following Controlled Product Use of Subject's OBCC (Outcomes Population)	CPPar1
Table 14.2.1.16	Statistical Summary of Baseline-Adjusted Plasma Nicotine Pharmacokinetic Parameters Cmax and AUCt Following Controlled Product Use (Outcomes Population)	CPStatSum
Table 14.2.1.17	Statistical Comparison of Baseline-Adjusted Plasma Nicotine Pharmacokinetic Parameters Cmax and AUCt Following Controlled Product Use (Outcomes Population)	CPStat1
Table 14.2.1.18	Nonparametric Statistical Comparison of Plasma Nicotine Pharmacokinetic Parameter Tmax Following Controlled Product Use (Outcomes Population)	CPStat2

Number	Title	Shell
Figure 14.2.2.1	Arithmetic Mean (SD) Unadjusted Plasma Nicotine Concentrations Versus Time Following Controlled Product Use (Linear Scale) (Outcomes Population)	PFPConc1
Figure 14.2.2.2	Arithmetic Mean Unadjusted Plasma Nicotine Concentrations Versus Time Following Controlled Product Use (Linear Scale) (Outcomes Population)	PFPConc2
Figure 14.2.2.3	Arithmetic Mean Unadjusted Plasma Nicotine Concentrations Versus Time Following Controlled Product Use (Semi-Log Scale) (Outcomes Population)	PFPConc3
Figure 14.2.2.4	Arithmetic Mean (SD) Baseline-Adjusted Plasma Nicotine Concentrations Versus Time Following Controlled Product Use (Linear Scale) (Outcomes Population)	PFPConc1
Figure 14.2.2.5	Arithmetic Mean Baseline-Adjusted Plasma Nicotine Concentrations Versus Time Following Controlled Product Use (Linear Scale) (Outcomes Population)	PFPConc2
Figure 14.2.2.6	Arithmetic Mean Baseline-Adjusted Plasma Nicotine Concentrations Versus Time Following Controlled Product Use (Semi-Log Scale) (Outcomes Population)	PFPConc3

# 14.2.2 Pharmacokinetic Figures – Plasma Nicotine

# 14.2.3 Subjective Effects Tables

## 14.2.3.1 Urge to Smoke Tables

Number	Title	Shell
Table 14.2.3.1.1	Summary of Urge to Smoke VAS Scores Following Controlled Product Use by Sex and Product (Outcomes Population)	UTSS
Table 14.2.3.1.2	Summary of Urge to Smoke VAS Score Differences from Pre-use to Following Controlled Product Use by Sex and Product (Outcomes Population)	UTSS
Table 14.2.3.1.3	Summary of Urge to Smoke VAS Parameters Following Controlled Product Use by Sex and Product (Outcomes Population)	UTSP
Table 14.2.3.1.4	Statistical Summary of Urge to Smoke VAS Parameters Emax and AUEC0-240 Following Controlled Product Use (Outcomes Population)	SUTSP

Number	Title	Shell
Table 14.2.3.1.5	Statistical Comparison of Urge to Smoke VAS Parameters Emax and AUEC0-240 Following Controlled Product Use (Outcomes Population)	SCUTS

#### 14.2.3.2 PES Subscales Tables

Number	Title	Shell
Table 14.2.3.2.1	Summary of PES Factor Scores Following Controlled Product Use by Product (Outcomes Population)	PESS

# 14.2.3.3 Intent to Use Tables

Number	Title	Shell
Table 14.2.3.3.1	Summary of Intent to Use VAS Raw Scores Following Controlled Product Use by Sex and Product (Outcomes Population)	ITUS
Table 14.2.3.3.2	Summary of Intent to Use VAS Bipolar Scores Following Controlled Product Use by Sex and Product (Outcomes Population)	ITUS
Table 14.2.3.3.3	Frequency of Intent to Use VAS Bipolar Scores in Each Category Following Controlled Product Use by Sex and Product (Outcomes Population)	ITUF

# 14.2.4 Puff Topography Tables

Number	Title	Shell
Table 14.2.4.1	Summary of Per-Product Puff Topography Parameters by Sex and Product (Outcomes Population)	PUFS
Table 14.2.4.2	Statistical Summary of Per-Product Puff Topography Parameters Following Ad Libitum Product Use (Outcomes Population)	SPUFS
Table 14.2.4.3	Statistical Comparison of Per-Product Puff Topography Parameters Following Ad Libitum Product Use (Outcomes Population)	SCPUF

# 14.2.5 Product Use Behaviour Tables

Number	Title	Shell
Table 14.2.5.1	Summary of Total Number of HTP/HHP Sticks Used During the Ad Libitum Product Use by Sex and Product (Outcomes Population)	PUBS
Table 14.2.5.2	Summary of Total Number of OBCCs Smoked on Days -1 through 5 During the Ad Libitum Product Use by Sex and Study Period (Outcomes Population)	SPUBS
Table 14.2.5.3	Summary of Total Number of Puffs During the Controlled Product Use by Sex and Product (Outcomes Population)	SCPUB

# 14.3 Safety Data Summary Tables

# 14.3.1 Displays of Adverse Events

Number	Title	Shell
Table 14.3.1.1	Product Use-Emergent Adverse Event Frequency by Product – Number of Subjects Reporting the Event (% of Subjects Who Received Study Product) (Safety Population)	CAES
Table 14.3.1.2	Product Use-Emergent Adverse Event Frequency by Product – Number of Adverse Events (% of Total Adverse Events) (Safety Population)	CAEE
Table 14.3.1.3	Product Use-Emergent Adverse Event Frequency by Product, Severity, and Relationship to Study Product – Number of Adverse Events (Safety Population)	CAESR

# 14.3.2 Listings of Deaths, other Serious and Significant Adverse Events

Number	Title	Shell
Table 14.3.2.1	Serious Adverse Events (Safety Population)	16.2.7

# 14.3.3 Narratives of Deaths, other Serious and Certain other Significant Adverse Events

Number	Title	Shell
Table 14.3.4.1	Out-of-Range Values and Recheck Results – Chemistry (Safety Population)	
Table 14.3.4.2	Out-of-Range Values and Recheck Results – Haematology (Safety Population)	CLBO
Table 14.3.4.3	Out-of-Range Values and Recheck Results – Urinalysis (Safety Population)	

